3.2. Respiratory Assessments at 36 Weeks PMA

A unique and important feature of the PROP protocol is the inclusion of physiologic biomarkers as potential predictors of respiratory morbidity up to 1 year of age. We have selected a set of respiratory assessments that evaluate different potential mechanisms of respiratory disease. Respiratory inductive plethysmography (RIP) assesses alterations in tidal breathing resulting from reduced lung compliance and airway obstruction.^{39, 40} Since infants with BPD and a history of

recurrent wheezing demonstrate airway reactivity in response to a bronchodilator,⁴¹ we will assess changes in tidal breathing in response to bronchodilator using RIP. Continuous pulse oximetry during RIP will enable us to detect mild oxyhemoglobin desaturations associated with brief central apneas during sleep, which are associated with reduced functional residual capacity.⁴² ⁴² To assess respiratory insufficiency under conditions of physical stress, continuous pulse oximetry will be performed during and shortly after oral feeding.

The above assessments will evaluate respiratory mechanics in the PROP cohort. However, some aspects of preterm respiratory disease may be more dependent on other alterations in respiratory function, such as ventilation/perfusion mismatch.⁴³ .⁴⁴ Infants who receive supplemental oxygen and/or flow via nasal cannula will undergo a standardized room air challenge to enable us to classify study participants according to the "physiologic" definition of BPD. Although the PROP investigators hope to improve upon the current definitions of BPD, we have designed our data collection tools and our respiratory assessments at 36 weeks PMA such that they will allow us to classify study participants according to all currently available definitions of BPD: (i) use of supplemental oxygen at 36 weeks PMA; (ii) NIH consensus definition; (iii) "physiologic definition.

Infants will receive these respiratory assessments dependent upon their respiratory status and on their ability to feed orally as shown in Figure 3.2.

Figure 3.2. Respiratory assessments at 36 weeks PMA: The RIP with its associated tests of oxygen saturations during sleep and oral feeding will be done on separate days.

Infants whose respiratory and/or feeding status made them ineligible for some or all of the 5 respiratory tests may become eligible if they are still in hospital at 40 ± 1 weeks PMA. Eligibility criteria will be the same as in Figure 3.2. In addition, infants who received RIP testing at around 36 weeks PMA while on nasal cannula will undergo repeat testing at 40 weeks PMA if they are in room air for at least 24 hours and still in hospital.

The permissible window for all tests is 34 to 41 weeks PMA with one exception: the permissible window for the trial of flow and oxygen reduction (room air challenge) is 35 to 37 weeks PMA. However, an infant who was not eligible for this test at 36 weeks PMA, or who received it but failed, should be re-tested at 40+/- 1 week PMA if eligible and still in hospital.

3.2.1. Trial of Flow and FiO₂ Reduction to 0.21 in Infants Receiving Nasal Cannula Flow With or Without Supplemental Oxygen (Room Air Challenge)

A consensus definition of BPD severity at 36 weeks PMA was developed during an NICHD/NHLBI Workshop held in June 2000.⁸ Mild BPD was diagnosed in preterm infants who are breathing room air at 36 weeks, after receiving at least 28 d of supplemental oxygen during their stay in the neonatal ICU. Infants receiving < 0.30 FiO2 at 36 weeks PMA were considered to have moderate BPD while severe BPD was defined as the need for ≥ 0.30 FiO2 or assisted ventilation (CPAP or mechanical ventilation). This clinical definition did not account for the variability in target SpO2 levels between clinicians and between hospitals. Walsh et al have evaluated a room air challenge test that aims to standardize the oxygen saturation target level on which a classification of oxygen dependency at 36 weeks PMA is based. Infants who were receiving low effective FiO2 < 0.30 by nasal cannula or hood (based on assumptions put forth by Benaron and Benitz and adapted by the STOP-ROP Trial⁵³) and who met specific SpO2 criteria, were challenged with an oxygen and flow reduction test.⁵⁴ The initial oxygen and flow reduction procedure included a stepwise reduction in oxygen by 2%, followed by a reduction in flow by 0.1 LPM increments. Following each reduction, infants were monitored for 10 minutes before the next weaning step. Cannula were removed when flow was discontinued and infants were monitored for 1 hour. Infants failed the challenge if SpO2 fell to < 88% for 5 mins, or < 80% for 1 minute. Twenty-four infants were studied and the diagnosis of BPD decreased from 36% to 24%, using the physiological definition instead of the clinical definition.⁵⁴ Infant SpO2 consistently reached equilibrium after 5 minutes of each wean and all infants who failed during the room air observation period did so in the first 30 minutes.

A follow up multicenter study used a slightly modified protocol.⁵⁵ Flow was weaned first, by 0.5 LPM increments (for flows 1.0-2.0 LPM), and then by 0.1 LPM increments down to 0.1 LPM. Then FiO2 was reduced in 20% increments, until room air was reached. Wean steps were shortened to 5 minutes and the room air observation period was reduced to 30 minutes. The SpO2 threshold for failure was increased to 90%. The test procedure was changed again from weaning FiO2 first and flow second to weaning flow first because this was thought to shorten

A detailed protocol and data collection instrument will outline the sequence of steps to safely conduct the test. Infants will be monitored continuously by pulse oximetry and vital signs before, during and after the test. If oxygen saturations are not maintained \geq 90%, the test will not progress and the infant will be returned to their baseline level of respiratory support, or support as needed.

3.2.2. Respiratory Inductive Plethysmography (RIP)

Physiologic measures of respiratory function such as forced expiratory flows and measurement of lung volume can be obtained using infant pulmonary function tests (PFTs), but the techniques require invasive procedures or sedation. Because one of the goals of PROP is to identify biomarkers that can easily be applied to clinical practice, we will use less invasive

respiratory physiologic measures that do not require sedation .

RIP is based on the principle that the output of the respiratory system can be assessed by measuring the excursion of the rib cage and abdomen and relies on the assumption that there are two degrees of freedom of the respiratory system.³⁹ This assumes that motion during respiration is only from inward and outward motion of the rib cage or abdomen, and not from motion in other directions or from rotation about the spine. Therefore, the change in volume of the rib cage and abdomen together should equal the change of volume of air in the lungs, or the volume of air moved during respiration.

Rib cage and abdominal motion are recorded by measuring the change in impedance with bands that are placed around the rib cage and abdomen (Figure 3.2.3.A). The bands consist of a wire coiled in a sinusoidal pattern through the length of the band. There is an electrical connection point at each end of the band through which a

Figure 3.2.3.A. 4 month old former 26 week GA preterm infant wearing RIP equipment. Flexible inductance bands are placed around the chest and abdomen and attached to a wireless transmitter. The receiver for the RIP signals is connected to a notebook computer [not shown] and data are recorded for analysis. The infant's shirt has been pulled up to allow visualization of the bands.

low voltage current is passed through the wires during recording. Changes in the volume of the rib cage and abdomen result in stretching of the bands and subsequent changes in inductance, which are stored in an external recording device.

RIP can be used to measure a variety of respiratory parameters.³⁹ Comparing the relative timing of maximal excursion of the rib cage and abdomen produces a measurement of thoraco-abdominal asynchrony (TAA). Using a pneumotachograph, RIP signals can be calibrated to provide volume and flow values. However, because volume calibration is not necessary to measure phase angle or the ratio of time to peak tidal flow versus total expiratory time, volume measurements will not be part of the PROP study. Flow measurements can be made by calculating the derivative of volume over time, and the ratio of the time to peak tidal expiratory flow to expiratory time (Tpef/Te) can be determined without volume calibration.

Tpef/Te has been found to be lower in infants with airway obstruction, and lower Tpef/Te is a risk factor for wheezing in the first year of life.^{20, 58}

Respiratory disease can result in TAA through a variety of mechanisms, including increased negative intrapleural pressure due to increased airway resistance or increased chest wall compliance. The phase angle

(ϕ) is a quantitative measure of TAA that is defined by the relationship ϕ =sin⁻¹(m/s), where m is the abdominal (AB) excursion at median rib cage (RC) excursion and s is the maximal AB excursion.³⁹ A plot of RC excursion vs. AB excursion (also known as a Konno-Mead plot) allows determination of m and s (Figure 3.2.3.B). In the absence of TAA, ϕ is zero, while paradoxical breathing represents maximal TAA, where ϕ =180°.

Although RIP was originally developed for adults with lung disease, it may be better suited for the study of infants. Infant chest wall compliance is much higher than that of older children and adults and therefore more easily deformed in the setting of lung disease.⁵⁹ This may make it easier to detect TAA. RIP has been used to demonstrate TAA in infants with BPD and airflow obstruction and in young children with acute upper airway obstruction.^{60, 61} There is a correlation between ϕ and direct measures of lung function, such as airway resistance. In young children with acute upper airway obstruction ϕ fell after administration of inhaled racemic epinephrine,⁶¹ suggesting that RIP can be used as an objective outcome measure of the effect of therapeutic interventions.

Bronchodilator Response

Bronchodilator response (BDR) is present in some preterm infants. In one small study, 6 of 10 infants with BPD demonstrated a decrease in ϕ after inhalation of albuterol,⁶² and in another larger study 67% of preterm infants had a fall in specific airway conductance after inhalation of a bronchodilator.⁶³ BDR in infants with BPD at 1 year of age is associated with a history of recurrent wheezing and lower lung function.⁴¹ These observations suggest some preterm infants may have increased smooth muscle tone which may be a risk factor for lower lung function and/or increased symptomatic respiratory disease. For these reasons, we will assess BDR at 36 weeks PMA using RIP. BDR will also be assessed at 1 year of age in a subset of infants; see section 3.3.3.

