4.8.1. Thoracoabdominal Asynchrony (Φ) as a Predictor of Post-discharge Hospitalization

We want to predict respiratory hospitalization using the phase angle Φ as measured during RIP testing. In order to estimate the sample size to achieve adequate power, we consider the hospitalization rate ranging from 30% to 50%. We also let the odds ratios (OR) for one standard deviation (SD) change in the Φ (1SD is about 40°)¹¹⁹ vary from 1.5 to 2.0 (both moderate effects). If we assume a conservative attrition rate of 10% (5% due to death and 5% due to loss to follow up), the total sample size required at the entry of the study in order to have 80% power to detect various odds ratios for hospitalization with a rate of 30-50% is shown in Figure 4.8.1. The required sample size decreases as either the hospitalization rate or the odds ratio to be detected increase. For example, to obtain 80% power to detect a significant association with OR of 1.5 (for one SD change of Φ) between Φ and hospitalization, we will require an initial sample size of 222, which after allowing for 5% post discharge mortality and 5% post discharge loss to follow-up will be an effective sample size of 200, at α = 0.05 using a two-tailed test when the hospitalization rate is 40%. We have chosen to attempt 253 evaluations of ϕ to be conservative (Table 4.8.1, hospitalization rate 30%, OR = 1.5).

Figure 4.8.1: Sample size required to obtain 80% power of detecting an association between Φ and respiratory hospitalization at a significance level of α = 0.05 (two tailed).

Table 4.8.1: Examples of sample sizes required to obtain 80% power of detecting a significant association between Φ and respiratory hospitalization

Hospitalization Rate	OR	Sample Size	
----------------------	----	-------------	--

30%	1.5	253
	1.7	248
40%	1.5	222
	1.7	130
50%	1.5	213
	1.7	124

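### The phase-angle formula in Protocol 3.2.2 returns only 0 to 90 degrees and cannot produce the 180 degrees that the same paragraph assigns to paradoxical breathing

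*Protocol*

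**What the plan says.** Section 3.2.2 introduces the phase angle phi as the measure of thoraco-abdominal asynchrony (TAA) from respiratory inductive plethysmography (RIP). It states that phi "is a quantitative measure of TAA that is defined by the relationship ϕ =sin⁻¹(m/s"). The two quantities in the ratio are explained in these words: "where m is the abdominal (AB) excursion at median rib cage (RC) excursion and s is the maximal AB excursion". According to the text, the Konno-Mead plot, which sets rib cage against abdominal excursion, "allows determination of m and s". The text names no other feature of the loop, such as its slope or direction.

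The paragraph then fixes the ends of the scale: "In the absence of TAA, ϕ is zero, while paradoxical breathing represents maximal TAA, where ϕ =180" degrees.

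Section 4.8.1 makes phi a named predictor: "We want to predict respiratory hospitalization using the phase angle Φ as measured during RIP testing". It plans on odds ratios per SD of phi ("1SD is about 40" degrees). For an odds ratio of 1.5 and a 40% hospitalization rate it says "we will require an initial sample size of 222". It then chooses 253 evaluations, which is the entry for a 30% rate. The bronchodilator part of section 3.2.2 cites earlier work in which response was seen as a fall in phi, and plans to assess response by RIP at 36 weeks.

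**The concern.** The formula and the stated scale cannot both hold. Because m cannot exceed s, arcsin(m/s) cannot exceed 90 degrees. In full paradox the loop closes to a line of negative slope, so m is 0 and the formula gives 0, the same value as perfect synchrony.

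The folding is not monotone. Once the values are folded, no later transformation can separate a true 30 from a true 150. Two uses are exposed:

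- **Prediction of hospitalization (4.8.1).** Tested infants with high asynchrony would be mixed with those who have little, which pulls the association towards the null.
- **Bronchodilator response measured by phi.** A hypothetical improvement from 150 to 110 degrees would be recorded as 180 − 150 = 30 rising to 180 − 110 = 70, an apparent worsening.

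**Working it through.** **1. What the formula returns.** Take rib cage RC = sin(t) and abdomen AB = sin(t − phi). RC is at its midpoint at t = 0 and t = π, where AB = −sin(phi) and +sin(phi). The loop width there is m = 2 sin(phi), and the full abdominal excursion is s = 2. Hence m/s = sin(phi), and arcsin(m/s) returns phi up to 90 degrees and 180 − phi beyond.

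| True phi | m/s | arcsin(m/s) | RC-AB correlation (sign = loop slope) |
|---|---|---|---|
| 0 | 0.000 | 0 | 1.00 |
| 30 | 0.500 | 30 | 0.87 |
| 60 | 0.866 | 60 | 0.50 |
| 90 | 1.000 | 90 | 0.00 |
| 120 | 0.866 | 60 | −0.50 |
| 150 | 0.500 | 30 | −0.87 |
| 170 | 0.174 | 10 | −0.98 |
| 180 | 0.000 | 0 | −1.00 |

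The stated 180 degrees is not reproduced. The sign of the slope separates the two halves: with 180 − arcsin(m/s) for negative slope, the last four rows return 120, 150, 170 and 180.

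**2. The plan's own sample size.** For one continuous covariate, n = (1.96 + 0.84)² / [p(1 − p)(ln OR)²].

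- p = 0.40, OR = 1.5: n = 198.9, so 199; 199/0.9 = 221.1, so 222. This matches the stated 222 (the protocol gives 200 as the effective number).
- p = 0.30, OR = 1.5: n = 227.3; 227.3/0.9 = 252.6, so 253. This matches the chosen 253.

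These figures depend on the odds ratio per SD, not on how phi is computed, so correcting the definition leaves them unchanged.

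**3. What the SD of 40 suggests.** On a 0 to 90 scale a uniform spread has SD 90/√12 = 26, and the largest possible SD is 45, with half the infants at each end. On 0 to 180 a uniform spread has SD 52. An SD of 40 therefore sits more easily on the longer scale.

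**4. Size of the loss if the formula is applied literally.** The protocol gives neither the mean of phi nor the share above 90, so both are assumed. Phi is taken as normal with parent SD 40, truncated to 0 to 180, with the parent mean varied. The true OR is 1.5 per SD of the truncated phi, the rate is 30% and n = 228 (253 less 10%). With r the correlation between folded and true phi, approximate power is Φ(√(n p(1 − p)) × ln 1.5 × r − 1.96). Unfolded: √(228 × 0.21) = 6.92; 6.92 × 0.405 = 2.81; Φ(0.85) = 80%.

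| Parent mean | Actual SD | Above 90 | r | Power |
|---|---|---|---|---|
| 20 | 27.9 | 6% | 0.93 | 74.5% |
| 40 | 31.7 | 12% | 0.85 | 66% |
| 60 | 34.9 | 24% | 0.65 | 45% |
| 80 | 36.7 | 41% | 0.26 | 11% |

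Fitting the logistic model to the folded values, in place of the correlation approximation, gives odds ratios of 1.46, 1.40, 1.28 and 1.07 and power of about 75%, 65%, 40% and 7%.

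**The case against.** The best defence is that the paragraph states its intent. The equation sin(phi) = m/s has two solutions between 0 and 180, and "while paradoxical breathing represents maximal TAA, where ϕ =180" degrees says which one applies in paradox. The planning SD points the same way. On this view the definition is compressed but not wrong. The rule for larger angles may be in Figure 3.2.3.B, which is not visible in the text available here, or in the manual of operations promised in section 3.3.6. Section 3.2.2 also mentions comparing the timing of maximal rib cage and abdominal excursion, which need not fold.

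Much of this stands. The intended scale is clear, and nothing shows that folded values are being used. What does not stand is that the text supplies the rule. The inverse sine returns one value, only m and s are named, and a programmer who codes the sentence gets the folded result. The over-reading in section 3.3.6 certifies recordings as research quality; it is not described as a check of the algorithm.

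A reader might also infer more than the protocol supports:

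- **That paradox is scored as 0.** No passage says so. It follows only if the formula is applied literally.
- **That the sickest infants look normal.** Section 4.2.1 generally counts infants ineligible for the tests, such as ventilated infants, as failures. The problem is confined to tested infants above 90 degrees.
- **That the association reverses.** Over the parent means tabulated it keeps its sign. The correlation turns negative only when most infants are assumed to exceed 90 (r = −0.26 at a parent mean of 100, with 59% above 90), and nothing in the protocol indicates that.
- **That an SD of 40 proves angles above 90.** It makes them plausible; the maximum of 45 on the shorter scale leaves 40 possible.

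**Conclusion.** The definition in section 3.2.2 is wrong as written: it yields 0 to 90 degrees and contradicts the 180 degrees in the same paragraph. The contradiction needs no outside assumption. Its practical size is uncertain. If the formula is applied literally, power for the analysis in section 4.8.1 falls from about 80% to between about 74% and about 10% as the assumed share above 90 rises from 6% to 41%. Those figures are illustrations: they rest on truncated-normal distributions whose actual SDs (28 to 37) are below the protocol's 40. If the software already separates the two halves of the scale, the loss is nil and only the text needs correcting.

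The point concerns one predictor in a study that describes itself as hypothesis generating. Section 4.8.1 uses a single component of the composite outcome. The other RIP index, Tpef/Te, does not use this formula. The primary outcome and the cohort size of 750 are not affected.

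**What to change.** In section 3.2.2, state that phi equals arcsin(m/s) when the Konno-Mead loop has positive slope and 180 degrees minus arcsin(m/s) when it has negative slope. This gives the 0 to 180 scale already described. Confirm that the analysis software applies this rule to the recorded RIP signals, and recompute any phi values, including bronchodilator changes, that were derived without it.

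The cost is one sentence and a software check. RIP signals are recorded for analysis, so recomputation should need no new data. The planned numbers in section 4.8.1 for an odds ratio of 1.5 (222 and 253) stay as they are.

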3.2.3. Oxygen Saturation During Oral Feeding

The assessment of oxyhemoglobin desaturation during feeding is designed to test the hypothesis that infants who have ventilatory instability manifested by lower oxygen saturations with feeding at 36 weeks PMA, corrected for change in minute ventilation with feeding, will be more likely to have clinical respiratory disease over the first year of life. This test will be done in conjunction with the RIP and sleep tests at 36 weeks PMA.

Preterm infants are at increased risk of desaturation with feeding. This is especially true in preterm infants with BPD,^{64, 65} bottle-fed infants,⁶⁶ infants with a nasogastric tube in place,⁶⁷ and in those infants with a lower baseline saturation before feeding.^{68, 69} The mechanisms of desaturation in these infants is unclear, but may be related to underlying cardiopulmonary disease, uncoordinated feeding patterns, gastroesophageal reflux, upper airway obstruction, or to impaired central control of respiration. Cardiopulmonary disease in preterm infants may be due to impaired alveolarization and abnormal pulmonary microvascular development resulting in decreased surface area for gas exchange,^{8, 17, 70} thickening of the gas exchange membrane as in fibrosis or edema,²¹ or ventilation and perfusion mismatch induced by fibrotic obstruction and narrowing of airway and vascular structures promoting pulmonary vascular shunting, both physiologic and pathologic from collateral circulation.⁷¹ Mechanisms of intermittent

hypoxemia with physical stress, such as with feeding or crying, include decreased ventilation⁷² or increased pulmonary blood flow. Decreased minute ventilation, due to decreased tidal volume, respiratory rate, or both, diminishes oxygen delivery to the alveoli. Increased blood flow with exertion decreases transit time of blood through the pulmonary capillary beds, thereby decreasing time of oxygen uptake. Normal pulmonary and cardiovascular function should provide adequate reserve to maintain normal oxygenation even under these conditions of stress. The physical stress of feeding may unmask otherwise clinically silent cardiopulmonary disease. We hypothesize that feeding preterm infants with diminished pulmonary and/or cardiovascular reserve will more easily and reproducibly quantify this diminished reserve than other unpredictable stressful events such as crying. The timing of feeding is predictable and the workload can be more easily quantified, e.g. as a volume of feeding for the infant's weight consumed over a defined period of time.

Previous studies have documented parameters of ventilation that may be abnormal during feeding in preterm infants; however, no attempts have been made to date to correlate the results of feeding studies with long-term respiratory outcome. A study of "healthy" preterm infants, born at mean 32.3 (+/- 0.4) wks CGA and studied at a mean 23 (+/- 3) days of life, demonstrated decreases in minute ventilation (Ve), respiratory rate (f), inspiratory time (Ti), and tidal volume (Vt), associated with the initial sucking burst during feedings, with recovery of all of these parameters, except for Ti, during the intermittent sucking phase of feeding.⁷² In these infants, the mean "workload" was a volume of formula consumed of 14 ml/kg over 14 minutes for the 34-35-6/7 wk infants, and 18 ml/kg over 10 minutes for the 36-38 wk infants. Oxygen saturations were not recorded in this study, but this workload was associated with significant changes in minute ventilation, primarily due to a reduced respiratory rate. Another study of preterm infants demonstrated a correlation between the severity and duration of desaturation events with feedings and the duration of apneic pauses.⁷³ Infants with both mild and severe BPD may experience tachypnea between sucking bursts.⁷⁴ In a study of healthy term infants, induced changes in feeding stimulus (increased volume of feeding by gravity) resulted in decreases in minute ventilation by only inducing a decrease in respiratory frequency, without a change in tidal volume.⁷⁵ Although it may be sufficient to measure changes in respiratory frequency during feeding to assess the relationship of ventilation to oxygen saturation, we will be able to measure relative changes in minute volume using the RIP equipment.⁷⁶ Utilizing the RIP equipment, we will calculate relative changes in minute ventilation from baseline and during feedings as a measure of change in the ventilatory pattern. Changes in oxygen saturation will be correlated with changes in minute ventilation from baseline, during and after feeding.

A detailed protocol and data collection instrument will outline the sequence of steps to conduct the Oxygenation with Feeding test. The study will be done with RIP impedance bands, electrocardiogram leads, and pulse oximeter in place. Data will be collected before feeding (2-3 minutes baseline in bed and then semi-upright in a standardized feeding position (approx 30-45 degree angle), continuously during PO feeding of a usual volume for the infant (minimal oral feeding volume criteria will determine eligibility for this test), and following feeding (2-3 minutes in semi-upright feeding position and then in the position in which the infant is normally placed after feeding). During each epoch, data from the recording oximeter will be

used to calculate mean SpO2, number of desaturations < 90% lasting for > 1 second duration, number of desaturations > 4% from baseline, lasting for > 1 second duration. The occurrence of clinically significant events that interrupt feeding will be recorded.

The proposed protocol, a noninvasive monitoring of feeding infants, poses minimal risk to the infants while having the potential benefit of identifying infants who are at greatest risk of developing post-prematurity respiratory disease.

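### Two of the three oximetry summaries of the feeding test are raw desaturation counts over a feed of unfixed length, so they mix event rate with observation time; mean SpO2 does not

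*Protocol*

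**What the plan says.** The Protocol specifies the summaries in section 3.2.3 itself. The calculation is made per epoch ("During each epoch, data from the recording oximeter will be") and the data are "used to calculate mean SpO2, number of desaturations < 90% lasting for > 1 second duration, number of desaturations > 4% from baseline", with a minimum duration of one second for an event. No rate, time below threshold or adjustment for epoch length is named.

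The epochs are defined as follows.

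- **Before feeding:** "2-3 minutes baseline in bed and then semi-upright in a standardized feeding position". The semi-upright part has no stated time of its own.
- **During feeding:** "continuously during PO feeding of a usual volume for the infant". The length depends on the infant's volume and speed.
- **After feeding:** "2-3 minutes in semi-upright feeding position and then in the position in which the infant is normally placed after feeding". The second position has no stated time.

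On interruptions, the section says: "The occurrence of clinically significant events that interrupt feeding will be recorded". It does not say how such an event bears on the counts.

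The background in the same section cites a study of preterm infants in which the mean intake was "14 ml/kg over 14 minutes for the 34-35-6/7 wk infants, and 18 ml/kg over 10 minutes for the 36-38 wk infants". It also argues for feeding as a stressor partly because workload can be expressed as volume per body weight over a defined time. Section 3.2 sets the age range for testing: "The permissible window for all tests is 34 to 41 weeks PMA with one exception".

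**The concern.** A count is a fair measure of how often an infant desaturates only if every infant is watched for the same time. Here the observation time is an outcome of the feed, and it plausibly varies with maturity and feeding skill. Three consequences follow for the two counts.

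1. Two infants with the same event rate get different values if one feeds more slowly.
2. An infant whose feed ends early has less time in which to accumulate events. If an adverse event ended it, the low count can be read as a good result.
3. A single long desaturation scores one event, and several brief dips score several.

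Aim 1 (section 2.2) asks whether the quantitative assessments made before discharge predict respiratory disease better than the BPD diagnoses. A predictor that carries feed duration as well as event rate would have a diluted association with the outcome and some confounding by maturity. The power statement in section 4.4.1 assumes no measurement error and no correlation between biomarker and covariates, and such a count strains both assumptions.

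**Working it through.** The Protocol gives no power, error rate or sample size for the feeding test, so there is no stated figure to reproduce. The check is of how the counts behave.

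**Feed length.** Expected count = event rate × duration. The durations are the two means cited in section 3.2.3, 14 and 10 minutes. Both age bands fall within the 34 to 41 week test window of section 3.2. The rates are illustrative: 33.3 per hour is the figure section 3.2.4 cites from a sleep study, and 10 and 60 per hour bracket it.

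| Rate per hour | 10 min | 14 min | Ratio |
|---|---|---|---|
| 10 | 10 × 10/60 = 1.67 | 10 × 14/60 = 2.33 | 1.40 |
| 33.3 | 33.3 × 10/60 = 5.55 | 33.3 × 14/60 = 7.77 | 1.40 |
| 60 | 60 × 10/60 = 10.0 | 60 × 14/60 = 14.0 | 1.40 |

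The rate cancels: 14/10 = 1.40, or 40% more events at an identical rate. Divided by observed minutes, the two feeds have the same expected value (ratio 1.0).

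**Shortened feed (assumed stopping time).** If a 14-minute feed ended at 5 minutes, the expected count at 33.3 per hour would be 33.3 × 5/60 = 2.77 against 7.77, or 5/14 = 36%. The 5 minutes is an assumption; the Protocol gives no stopping times.

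**Sustained against intermittent desaturation (constructed traces).** Take a 10-minute (600-second) feed, baseline 96%, falling to 86%.

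- One episode lasting 580 s: count 1; time below 90% = 580/600 = 96.7%; mean SpO2 = (20 × 96 + 580 × 86)/600 = 86.3%.
- Ten dips of 5 s: count 10; time below 90% = 50/600 = 8.3%; mean SpO2 = (550 × 96 + 50 × 86)/600 = 95.2%.

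On these traces the count more than 4% below baseline equals the count below 90%. Both counts rank the sustained trace as the better one. Mean SpO2 and percent of time below 90% rank it as the worse one.

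**Dilution under assumed spreads.** A Poisson simulation used a mean feed of 12 minutes, a mean rate of 33.3 per hour, and independent log-normal variation between infants in rate and duration. The entries are correlations.

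| CV of rate | CV of duration | Count with true rate | Same, all feeds 12 min | Count with duration |
|---|---|---|---|---|
| 0.5 | 0.2 | 0.75 | 0.79 | 0.30 |
| 0.5 | 0.5 | 0.59 | 0.79 | 0.59 |
| 0.9 | 0.2 | 0.89 | 0.92 | 0.20 |
| 0.9 | 0.5 | 0.76 | 0.92 | 0.42 |

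The loss runs from slight to substantial, depending on a spread of durations that the Protocol does not give.

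**The case against.** The strongest reply is that the counts are not the whole test. Mean SpO2 stands first in the same sentence; it does not grow with feed length, and it falls under sustained hypoxaemia. The hypothesis in section 3.2.3 concerns lower saturations corrected for change in minute ventilation, not a number of events. No overall score is defined. Sections 4.5 and 4.7 leave the creation of summary variables and the detail of individual analyses to a later stage, and a separate detailed test protocol is mentioned but not shown. Because recording is continuous, nothing is lost and rates remain derivable.

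Most of this stands, and it rules out several stronger readings that a reader might infer.

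- **That the test as a whole ranks continuous hypoxaemia as mild.** It does not: mean SpO2 puts the sustained trace in the right order.
- **That the feeding count is several times the baseline count by construction.** Setting a 10 to 14 minute feed against 2 to 3 minutes would suggest 10/3 = 3.3 to 14/2 = 7 times. However, the before and after epochs include untimed segments, so their total length is unknown, and the Protocol does not say that raw counts will be compared across epochs.
- **That 40% is the bias in this cohort.** The 14 and 10 minutes come from infants described as healthy, born at a mean of 32.3 weeks, who took different volumes. This cohort is born at 23 0/7 to 28 6/7 weeks.
- **That interrupted feeds go unnoticed or always score low.** Interrupting events are recorded, and a feed that pauses and resumes may lengthen the epoch.

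What the reply does not remove is that section 3.2.3 names the derived measures and gives two of them without a denominator. The separate test protocol is described as covering the steps for conducting the test. The adjustment in section 4.6.2 includes gestational age and birth weight but does not name feed duration.

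**Conclusion.** The point holds for the two desaturation counts only. As written, each combines event rate with the length of the feed, each can fall when a feed is cut short, and each records one sustained desaturation as a single event. The direction follows from the definitions and needs no assumption beyond an event rate that does not depend on feed length. The 40% figure is an illustration from a more mature population, and the simulated correlations rest on assumed spreads. The size in this cohort cannot be stated.

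The stakes are modest. The feeding test is one candidate predictor in a study that sections 4.1 and 4.6.4 describe as hypothesis generating. The primary outcome definition and the sample size are unaffected. It is worth correcting because the better measures come from data already being collected.

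**What to change.** In section 3.2.3:

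1. Keep mean SpO2 for each epoch.
2. Replace the two counts with desaturations per minute of observed epoch time, using the same two event definitions.
3. Add percent of epoch time with SpO2 below 90% and percent of epoch time more than 4% below baseline. A rate alone still counts a sustained episode once, so both kinds of measure are needed.
4. Report feed duration with these measures.
5. Flag feeds ended early by a recorded clinically significant event, and examine them in a sensitivity analysis so that a truncated observation is not read as a better result. Making such feeds a fixed worst category is not advised: section 3.2.3 lists uncoordinated feeding and reflux among the possible mechanisms of desaturation, and a forced rank could bring in the feeding-skill confounding that the change is meant to reduce.

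The cost is small. Oximetry is already continuous, per-epoch summaries already require the start and end of each epoch, and interrupting events are already recorded. The form may need one item to separate a feed that ended from one that paused and resumed. A rate from a very short feed will be imprecise, which is a further reason to report duration beside it.
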